B-cell responses to viral infections serve to protect from the initial challenge, and to provide extended immunity against reinfection. After encountering antigen, activated antigen-specific B-cells proliferate and differentiate into either antibody secreting cells (ASCs, or plasma cells), or become long-lived memory B-cells. Recombination of VDJ genes and somatic hypermutation of activated B-cells committed to become memory B-cells, leads to the generation of diverse B-cell repertoires with higher affinity for target antigens. Plasma cells formed during the acute and convalescent phases continue to secrete antibodies, giving rise to serological memory following acute infection. Memory

B-cells formed during the primary infection constitute the second arm of B-cell memory. Memory B-cells respond quickly to reinfection by generating new high-affinity plasma cells. Long-term protection is achieved through the induction of both long-lived plasma cells and memory B-cells. The activation and differentiation of virus specific B-cells during and after infection impacts the functional quality, magnitude and longevity of antibody responses and the capacity to response to re-infection. Memory B-cell responses to other CoVs, including SARS-CoV-1, are relatively short-lived, which may explain why immunity to these infection wanes over the period of a few years. As such, it is imperative that we describe in detail the B-cell response to SARS-CoV-2 in samples from different patient groups.

We will therefore take sequential samples from study participants with confirmed SARS-CoV-2 infection throughout the study, describing the nature and duration of the antigen-specific B-cells. This protocol will allow researchers to determine the type of differentiation of antigen-specific B-cells into antibody secreting cells and memory B-cells and describe the duration of this memory B-cell response. The results of this analysis will provide critical insight into the duration and nature of the immune response to SARS-CoV-2, enabling assessment of future potential vaccines and their implementation. Furthermore, this data will allow accurate modelling of global SARS-CoV-2 transmission dynamics and assessment of non-pharmaceutical interventions.

Antibody Responses

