METHODOLOGY

This is a longitudinal observational cohort study of individuals, seeking to define the immunological memory immune response following SARS-CoV-2 infection. Sequential observations and clinical samples will be taken from individuals who have had SARS-CoV-2 infection as determined by positive antibody response, regardless of disease severity and as determined by symptoms, government testing or antibody testing as part of ALSPAC. Individuals who have not had infection with SARS-CoV-2 will be recruited as controls, and these participants will undergo the same sequential observations and clinical sampling procedures. The samples obtained from this protocol will then be analysed to examine the immune response to SARS-CoV-2, to determine whether robust long-lived immunological memory to SARS-CoV-2 is established, how long it persists after recovery from COVID-19 and how this is influenced by a range of different factors and clinical phenotype.

This study will use the Avon Longitudinal Study of Parents and Children (ALSPAC – also known as Children of the 90s by participants and the public) to recruit participants. Between April 1991 and December 1992 ALSPAC recruited more than 14,000 pregnant women into the study and these women (some of whom had two pregnancies or multiple births during the recruitment period), the children arising from the pregnancy, and their partners have been followed up intensively over two decades and we hold detailed historical data and biological samples for these participants with consent for use in future research. The original study mothers and their partners are referred to as the G0 cohort. The original offspring and now their partners are referred to as the G1 cohort.

Participant Selection

ALSPAC have undertaken 5200 serological SARS-CoV-2 tests on G0 and G1 cohort participants and administered questionnaires to participants during the pandemic. In order to achieve the research objectives outlined in this protocol, in each clinic round this study will aim to recruit:

- All G1 individuals and a comparator sample of G0 individuals meeting eligibility criteria who meet the study definition of cases
- Up to 200 G1and G0 individuals meeting eligibility criteria who meet the study definition of controls

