Information from these along with linked NHS medical records data will be used to identify potential participants. Based on seroprevalence estimates, ALSPAC cohort size, and estimations of typical response to similar studies, this study therefore estimates recruiting approximately:

- 100 cases of previous SARS-CoV-2 infection at Visit 1 (approx. upper limit of 250 cases)
- 100 control individuals without previous SARS-CoV-2 infection age, sex and symptom matched to cases and 100 random controls without previous SARS-CoV-2 infection (approx. upper limit of 250 controls)

Where needed (i.e. if there are large numbers of potential cases), priority will be given to participants with pre-pandemic measures of BMI and lung function (objectively assessed at the age of 24 years) and previous biological samples.

[figure not shown]
As part of an initial visit, blood will be taken and the antibody and T-cell response to SARS-CoV-2 determined. Individuals who are cases with a SARS-CoV-2 antibody response and/or a positivie T-cell response will be enrolled in the SARS-CoV-2 arm. Individuals who are cases with information available that there is no detectable SARS-CoV-2 antibody or T-Cell response will be considered seronegative and will not be required to participate further in the study. Individuals who are recruited as controls and have a confirmed SARS-CoV-2 antibody negative response will be enrolled into the control arm for two remaining visits, sufficient negative controls will be recruited to allow for the possibility that some controls will become infected with SARS-CoV-2 during the duration of the study and will not be eligible to complete all four visits. Those who were initially recruited as controls

who have subsequently tested positive will also be retained in the study and will move from control arm to case arm as appropriate. Where cases are no longer available, but new cases are defined, sample size will be maintained by the recruitment of new case events.

Pilot study

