- (9) Assess prevalence of cross-reactivity against circulating CoVs and how this might influence the outcome of response to COVID infection.
- (10) Assess changes in the exercise capacity test, SF36 and self-reported dyspnoea during the convalescent period.

Study design

This is a longitudinal observational cohort study of adults within the Bristol area, conducted on individuals who may fall into the following groups of patients:

- (1) healthy seronegative controls (some of whom may become infected during the study),
- (2) asymptomatic/pauci-symptomatic
- (3) symptomatic infection not requiring hospitalisation,
- (4) moderate illness not requiring hospitalisation,
- (5) hospitalised patients who did or did not require mechanical ventilation

Sampling framework

Current estimates of COVID-19 prevalence in the SW England (based on seroprevalence data) range between 2-6%, with age and time since infection contributing to differences in patient groups. It is therefore reasonable to assume that seroprevalence is approximately 3%. ALSPAC have undertaken 5000 serological SARS-CoV-2 tests on cohort participants; therefore, if only 3500 of these are returned, we would expect to identify 100 individuals seropositive to SARS-CoV-2. If only 50% of these 100 individuals wish to enter into this study, the cohort of seropositive individuals would be 50.

The number of seropositive individuals will be increased by incorporating ALSPAC cohort individuals who:

- 1. self-report as being highly likely to have had COVID-19 infection (from either positive SARS-CoV-2 PCR test performed at NHS care facility, COVID-19 testing site or home testing), **OR**
- 2. have been told by a physician that, in the opinion of that doctor, they have had a clinical illness likely to be COVID-19 **OR**
- 3. based on a combination of symptoms they are likely to have been cases

DATA COLLECTION

Cases - inclusion criteria

This study will be undertaken on participants of the ALSPAC cohort meeting the following criteria:

- 1. Aged 25 or over, AND
- 2. Individuals who have undergone SARS-CoV-2 antibody testing through the ALSPAC SARS-CoV-2 serology study (IRAS 289493), **OR**
- 3. Individuals who self-report or through linkage to official health records as being highly likely to have had COVID-19 infection (from either positive SARS-CoV-2 PCR test performed at NHS care facility, COVID-19 testing site or home testing), **OR**

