ELISAs and Western Blots will be used to quantify titres of each antibody isotype (e.g. IgM, IgA, IgG) specific to SARS-CoV-2 viral proteins/epitopes being produced including (but not limited to) the spike glycoprotein, the receptor binding domain (RBD) and nucleoprotein. Techniques such as UREA based ELISA or surface plasmon resonance (SPR), will be used to determine the extent of antibody affinity maturation by calculating the avidity index of antibodies towards the spike glycoprotein and RBD over time (Mann et al. 2014). The neutralising activity of antibodies will be measured using techniques such as a high-throughput pseudovirus neutralization assay using SARS-CoV-2 spike protein pseudotyped lentiviral particles or SARS-CoV-2 microneutralisation assays with live virus.

Analysis of the B-cell response:

To describe the dynamics of the B-cell response we will enumerate and characterise antibody secreting cells (ASCs/plasma cells/plasmablasts), activated B-cells (ABCs) and memory B-cells

(MBCs) at various timepoints. This will be achieved using a combination of techniques which will include (although are not limited to) flow cytometry (via fluorescently labelled viral antigens and markers for ASCs, ABCs versus MBCs, etc.), B-cell ELISpots (Ellebedy et al. 2016; Clutterbuck et al. 2012) and antigen specific B-cell proliferation assays. The heterogeneity and degree of somatic hypermutation (SHM%) in SARS-CoV-2 specific B-cell responses will be determined by B-cell repertoire sequencing using RNA from PBMC and will identify 'public' versus 'convergent' B cells.

In-depth analysis of T-cell responses:

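### Antibody positivity is taken as infection with no false-positive allowance at about 3% seroprevalence, and the either-marker rule at Visit 1 may keep persistent cross-reactive signals in the SARS-CoV-2 arm

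*Protocol*

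**What the plan says.** The Methodology section describes the target population as "individuals who have had SARS-CoV-2 infection as determined by positive antibody response"; the same sentence goes on to mention symptoms, government testing and ALSPAC antibody testing. The background section on B-cell immunity speaks of taking "sequential samples from study participants with confirmed SARS-CoV-2 infection".

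The Sampling framework starts from prevalence estimates for the region ("based on seroprevalence data) range between 2-6" per cent) and settles on one value: "It is therefore reasonable to assume that seroprevalence is approximately 3" per cent. From this it derives the yield of the serology survey: "if only 3500 of these are returned, we would expect to identify 100 individuals seropositive to SARS-CoV-2". It then applies an uptake rate: "If only 50% of these 100 individuals wish to enter into this study, the cohort of seropositive individuals would be 50". Cases are to be added from people with a reported positive PCR, a physician's opinion or a suggestive combination of symptoms.

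Participant Selection forecasts, from seroprevalence, cohort size and expected response, about "100 cases of previous SARS-CoV-2 infection at Visit 1". At Visit 1 a case enters the SARS-CoV-2 arm if antibody, T-cell response or both are positive. A case with neither leaves the study.

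No sensitivity, specificity or false-positive allowance appears in either section. Yet cross-reactivity with common-cold coronaviruses is discussed under Antibody Responses, is the subject of secondary objective 9, and is to be measured under Additional Assays.

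**The concern.** When about 97% of those tested are uninfected, the number of false positives is driven by the uninfected majority. A small false-positive rate can then make up a large part of a small group of positives. The forecasts say nothing about this.

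The Visit 1 rule bears on the primary objective, which is the magnitude and duration of immunological memory. A never-infected person whose false signal is random will usually fail the re-test and leave. A person whose signal comes from a stable cross-reactive antibody or T-cell response can pass on that one marker and stay positive at later visits. The filter therefore tends to keep the errors that look most like durable memory. A smaller number who pass by chance and later turn negative would read as memory lost. Both blur the persistence estimate and the comparisons by clinical phenotype.

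**Working it through.** **Inputs from the protocol.** Sampling framework: 3500 returned tests, seroprevalence about 3% (range 2–6%), 100 expected positives, 50% uptake. Participant Selection: entry on either marker.

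**Assumed, because the protocol gives no value.** f = false-positive rate of the survey test; Se = its sensitivity; a = chance that a false antibody result recurs at Visit 1; t = chance that a never-infected person has a positive T-cell result.

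**1. The plan's own figures.** 3500 × 0.03 = 105, against 100 stated. Since 100/3500 = 2.86%, which rounds to 3%, the gap is rounding. 100 × 0.5 = 50 reproduces exactly.

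**2. If 3% is the share testing positive.** True prevalence p = (0.03 − f)/(Se − f), false positives = 3500 × (1 − p) × f, and share = false positives/105. For f = 1% and Se = 1: p = 0.02/0.99 = 0.0202; 3500 × 0.9798 × 0.01 = 34.3; 34.3/105 = 33%. At Se = 0.8 the share is still about 33%.

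**3. If 3% is true prevalence.** True positives = 105 × Se, false positives = 3500 × 0.97 × f = 3395 × f. For f = 1% and Se = 1: 33.95/(105 + 33.95) = 24%. With Se = 0.9 it is 33.95/128.45 = 26%, and with Se = 0.8 it is 33.95/117.95 = 29%. The expected number of positives would then be about 118 to 139, not 100.

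With Se = 1:

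| f | 3% = share testing positive | 3% = true prevalence |
|---|---|---|
| 0.2% | 6.8/105 = 6% | 6.8/111.8 = 6% |
| 0.5% | 17.1/105 = 16% | 17.0/122.0 = 14% |
| 1% | 34.3/105 = 33% | 34.0/138.9 = 24% |
| 2% | 69.3/105 = 66% | 67.9/172.9 = 39% |

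At f = 1%, moving from 2% to 6% (the protocol's own range) takes the share from 49% to 16% on the first reading and from 33% to 14% on the second.

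**4. Visit 1.** A never-infected survey positive stays with probability k = 1 − (1 − a)(1 − t). Take the plan's 100 positives and f = 1%. Then p = (0.0286 − 0.01)/0.99 = 0.0188, and 3500 × 0.9812 × 0.01 = 34.3 are false. If every truly infected person stays, the share after Visit 1 is 34.3k/(65.7 + 34.3k).

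| a | t | k | Never-infected share after Visit 1 |
|---|---|---|---|
| 1% | 1% | 2% | 1% |
| 1% | 5% | 6% | 3% |
| 10% | 20% | 28% | 13% |
| 50% | 50% | 75% | 28% |
| 100% | any | 100% | 34% |

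**5. Dilution by other routes (illustration).** Suppose the 50 survey recruits carry the same 34.3% (17.15 false, 32.85 true) and 50 more cases come by other routes, all truly infected and all staying. The share of the arm is 17.15k/(82.85 + 17.15k). For k = 6%, 28%, 75% and 100% this is about 1%, 5%, 13% and 17%. Misdiagnosed cases among the other routes would raise it.

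**The case against.** The case on the other side is substantial.

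- A reader might infer that the plan counts 100 survey positives as 100 infected people. The Sampling framework does not say so. It calls them seropositive and carries 50 forward. The 100 cases in Participant Selection are a separate forecast that also rests on cohort size and response. What stands is that this forecast uses seroprevalence without correction and labels the result previous infection.
- A reader might infer that Visit 1 leaves false positives untouched. It does not: anyone negative on both markers leaves, and if errors are independent between samples only about 2–6% of false positives remain. What stands is that the rule gives little protection against a signal that belongs to the person, which is the mechanism the protocol itself names.
- The survey belongs to a separate study whose assay and any confirmatory step are not described here, so 1% is only one point in a range.
- The word confirmed occurs in background text, and Infection Control Measures speaks of possible or confirmed infection. The labelling is therefore inconsistent rather than uniformly wrong.
- Pre-exposure samples, several antigens, neutralisation and cross-reactivity assays are already planned, and the choice of analysis set may be left to an SAP. That shows the remedy is within reach. But the infection definition, the arm-entry rule and the forecasts are fixed in the protocol, and none of them uses these data.

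**Conclusion.** The point holds in a limited form. The protocol equates antibody positivity with infection, forecasts infected cases with no false-positive allowance, and enters cases into the arm on one positive marker of two. Among survey positives, the never-infected share runs from about 6% to 66% (3% as the share testing positive) or about 6% to 39% (3% as true prevalence, full sensitivity), for assumed false-positive rates of 0.2% to 2%.

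It would be wrong to conclude that a third of the SARS-CoV-2 arm was never infected. That figure needs a 1% false-positive rate, the first reading of 3%, full recurrence at Visit 1 and no cases from other routes. The documents establish none of the first three, and the plan to add PCR, physician and symptom cases contradicts the last. What remains is a risk of unknown size that the entry rule concentrates in persistent false signals, in a study whose primary objective is persistence.

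**What to change.** Keep the either-marker rule for follow-up, so that nobody is excluded, and grade each case by strength of evidence:

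- **Confirmed:** a positive PCR; or a rise over the participant's own stored pre-pandemic sample, where one exists with consent (see Use of existing ALSPAC samples in this study); or antibody to both spike/RBD and nucleoprotein in the same sample. The laboratory section already plans to measure "the spike glycoprotein, the receptor binding domain (RBD) and nucleoprotein".
- **Single-marker:** all other cases in the arm.

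Report the persistence results for all cases and for confirmed cases side by side. Confirmed cases should not be the only primary set, because the two-antigen route favours people with broader responses, which is itself related to the outcome. State this limitation and the loss of precision. Read any rise over baseline together with the vaccination dates collected in the questionnaire.

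State explicitly that the 100 in the Sampling framework are expected test positives. Give the Participant Selection case forecast with a false-positive range under a stated assay specificity, and say whether 3% means the share testing positive or true prevalence.

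The cost is a definition, a second set of results, assays on some stored samples and lower precision in the confirmed group. No visit is added.

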- 4. Individuals who have been told by a physician that, in the opinion of that doctor, they have had a clinical illness likely to be COVID-19.

Control participants – inclusion criteria

- 1. Aged 25 or over, AND
- 2. Individuals who self-report as not experiencing symptoms of COVID-19 via the symptom survey and do not have case status through linkage to official health records, **AND**
- 3. Self-report as not having had positive SARS-CoV-2 molecular test, AND
- 4. Are confirmed SARS-CoV-2 seronegative at Visit 1 and then at visit 2

Exclusion criteria for both controls and cases

- 1. Do not wish to participate in this research study
- 2. Participants taking blood thinners (e.g. warfarin) or with a known clotting disorder
- 3. Do not meet eligibility criteria for respective arm

Invite procedure

An initial invitation email (*Initial invite v2*), and link to a participant information sheet (*Information Sheet v2*) will be sent to eligible participants, via contact details held, with participant consent, in the ALSPAC contact management system. Appointments will be offered on a range of days and times, including weekends. Participants will be able to respond by telephone or email. A reminder email will be sent if there is no response after one weeks (*Reminder email v2*) and if they do not respond after a further week they will be called by a member of the ALSPAC research team. This is an invitation procedure used previously within ALSPAC and study participants are familiar with contacts from the study by these methods.

Following the initial visit, samples will be analysed for current serological response. Those cases who are seropositive or T-Cell positive at Visit 1 and all controls whether confirmed as seronegative or seropositive will be invited (*follow up invite v2*) to complete repeat visits 4 months, and 8-12 months post visit 1. Those not eligible to continue the study will be notified by email (*follow up no visits v2*).

Where cases are no longer available, but new cases are defined, sample size will be maintained by the recruitment of new case events.

Before the clinic visit - (Visits 1-4)

Once booked for an appointment, the participant will be sent a confirmation email (*Confirmation letter v1, with a link to visiting children of the 90s COVID-19 information sheet*) and then an appointment reminder call the day prior to their appointment this will include a check for any current COVID-19 symptoms.

At the clinic visit

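### Control inclusion criterion 4 makes baseline control status depend on a serology result about 4 months later, which conflicts with the protocol's own enrolment, retention and invitation rules

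*Protocol*

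**What the plan says.** Five places in the protocol bear on who is a control and for how long.

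- **Control participants – inclusion criteria**, item 4, joined to the other items by AND: controls "Are confirmed SARS-CoV-2 seronegative at Visit 1 and then at visit 2".
- **Exclusion criteria for both controls and cases**, item 3: "Do not meet eligibility criteria for respective arm".
- **Participant Selection**: recruited controls who "have a confirmed SARS-CoV-2 antibody negative response will be enrolled into the control arm for two remaining visits". Extra negative controls are to be recruited because "some controls will become infected with SARS-CoV-2 during the duration of the study and will not be eligible to complete all four visits". The next sentence says that people who entered the study on the control side "who have subsequently tested positive will also be retained in the study and will move from control arm to case arm as appropriate".
- **Invite procedure**: "all controls whether confirmed as seronegative or seropositive will be invited" to the repeat visits, which are set at 4 months and at 8-12 months after Visit 1.
- **Study design**, group 1: "healthy seronegative controls (some of whom may become infected during the study").

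**The concern.** An inclusion criterion should be decidable at inclusion. This one is decided about 4 months later. Nobody can be confirmed as an eligible control at Visit 1, and whether a person's Visit 1 sample counts as a control sample depends on what happens to that person afterwards. The resulting control group consists of people who stayed uninfected and kept attending, which is selection on a post-enrolment outcome.

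Two kinds of data are at stake. The first is valid Visit 1 control data from people who later seroconvert or miss Visit 2. The second is the clear handling of controls infected between visits. These participants have a pre-infection sample taken within the study and an infection date bounded by two visits, which is useful for a study of how immune memory arises and lasts. Controls also serve as comparators in immune profiling and, if numbers allow, for the key outcomes.

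**Working it through.** The point rests on comparing rules. No stated sample size, power or alpha is involved, so there is no figure of the plan to reproduce.

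**Step 1: when is control status set?**
- Inclusion criterion 4: after two negative results, the second at Visit 2, 4 months after Visit 1.
- Participant Selection: after the negative antibody result at the initial visit, with two visits still to come.
- Infection Control Measures: controls are described as confirmed negative after Visit 1.

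The second and third agree with each other and not with the first.

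**Step 2: what happens to a control who is seropositive at Visit 2?**
- Criterion 4 with exclusion 3: the person does not meet the control criteria and is excluded from that arm, Visit 1 included.
- Participant Selection: the person is retained and moves to the case arm.
- Study design: infection during the study is expected within the control group.

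Under the last two rules the person was a control at Visit 1 and became a case later. Under the first the person never was a control.

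**Step 3: what happens to a control who misses Visit 2?** Criterion 4 can never be confirmed. No other section says that such a person's Visit 1 data are lost; this follows only from reading criterion 4 as written.

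**Step 4: what happens to a control who is antibody-positive at Visit 1?** Participant Selection enrols only antibody-negative controls, and its switch rule covers those who test positive subsequently. Invite procedure still recalls Visit 1 seropositives. Their arm is not stated.

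**Step 5: what does seronegative refer to?** Vaccination is recorded at the repeat visits, and the antibody assays include spike and the receptor binding domain. Criterion 4 names no antigen, so a vaccinated and uninfected control could fail it at Visit 2.

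**Step 6: illustration of size.** Planned controls: 100 matched + 100 random = 200 (Participant Selection). The share *p* seroconverting between Visits 1 and 2 is an assumption; the protocol gives none. Number failing = 200 × *p*; number left = 200 × (1 − *p*); number needed at Visit 1 to keep 200 double-negative controls = 200 / (1 − *p*), rounded up.

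| Assumed *p* | Fail criterion 4 | Left | Needed at Visit 1 |
|---|---|---|---|
| 2% | 4 | 196 | 205 |
| 5% | 10 | 190 | 211 |
| 10% | 20 | 180 | 223 |
| 20% | 40 | 160 | 250 |

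Missed visits come on top. If 15% to 20% of controls missed Visit 2 (also an assumption), 200 × 0.15 = 30 to 200 × 0.20 = 40 could not be confirmed.

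**The case against.** A reader might infer that the protocol gives infected controls two opposite fates, because Participant Selection calls them ineligible to complete all visits and then retains them. The text does not force that reading. The first clause explains why spare negative controls are recruited, and the two sentences fit together if it means that such people will not complete all visits *as controls*. Participant Selection, Study design and Invite procedure all point towards keeping them. What stands is that the qualifying words are missing, so the clause is loosely drafted.

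A reader might also infer that exclusion 3 removes infected controls from the study. That is not established. The exclusion refers to the respective arm, which after reassignment is the case arm. The case criteria can be met by having been tested in the ALSPAC serology study or by a reported positive PCR. The exclusion does bite on their standing as controls at Visit 1.

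The consequences are limited too. The primary objective is descriptive, comparison with controls is only a possibility under Descriptive analysis of other measures, and stored earlier samples may supply a pre-exposure baseline where consent exists. The study flow diagram is not available in the text reviewed and might stage control status by visit. None of this reconciles the written criterion 4 with enrolment on the Visit 1 result.

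**Conclusion.** The concern holds for criterion 4. It is a stated rule that contradicts the enrolment, retention and invitation rules elsewhere in the protocol, so it is not a detail left for an analysis plan. Applied literally with exclusion 3, it conditions control membership on a future outcome and discards valid Visit 1 control data from those who seroconvert or miss Visit 2. The wording on completing all visits is a lesser, related drafting fault.

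The number of participants affected cannot be derived from the protocol; the table above depends wholly on assumed rates. The contradiction itself needs no rate. It would be wrong to conclude that a primary test is invalidated or that infected controls are certain to be lost.

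**What to change.** 1. In control inclusion criterion 4, delete the Visit 2 condition, so that control status is set on Visit 1 data.
2. In Participant Selection, reword the clause on infected controls to say that they will not complete all visits as controls.
3. Add one rule: a control counts as a control up to the first evidence of infection (a molecular test, or antibody not attributable to vaccination) and as a case from that dated visit onward.
4. State that the same evidence decides the arm of controls who are antibody-positive at Visit 1, and word criterion 4 and exclusion 3 to agree with it. These people should not all be labelled asymptomatic cases: some controls are symptom-matched to cases, and some antibody may come from vaccination.

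Person-time or interval-censored analysis is not needed, since no listed objective calls for it. The cost is protocol wording and one dated arm variable in the dataset. No visits are added, because all controls are already invited back.
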